6.4 Determination of the MTD and RP2D

Dose limiting Toxicities (DLTs):

DLTs will be assessed in the phase Ib portion of the trial. DLTs will be collected during the run-in (dose 1 of ONC201), cycle 1 and prior to dosing cycle 2 day 1. All patients in a cohort must be assessed for DLTs through pre-dosing cycle 2 day 1 prior to the next cohort being opened.

Dose Definitions (MAD, MTD, RP2D)

The maximally tolerated dose (MTD) is defined as the dose frequency schedule above which the absolute observed DLT rate is $> 25\%$. The MTD is equivalent to the anticipated recommended phase 2 dose (RP2D).

However, the final RP2D may also be influenced by pharmacokinetic information, additional emerging toxicity data, pharmacodynamic data, or practical dosing (capsule load) information. The RP2D will never exceed the MTD.

The MAD, or maximally administered dose, is estimated to be 625 mg (5 capsules) given weekly, beginning day -7 (phase Ib) and day 1 (phase II).

6.4.1 Dose Limiting Toxicity (DLT) definition

Toxicity will be evaluated according to the NCI CTCAE, version 5.0.

DLTs will be collected during the run-in (dose 1 of ONC201), cycle 1 and prior to dosing cycle 2 day 1. All patients in a cohort must be assessed for DLTs through pre-dosing cycle 2 day 1 prior to the next cohort being opened.

If, however a patient experiences one of the below toxicities after cycle 2 or in the phase II portion it will not be considered a DLT, however: hold treatment (both drugs), once the toxicity reduces to a grade 1 or less, dose reduce (ONC201) and resume treatment, even though it will no longer be defined as a DLT.

A DLT will be defined as any of the following AEs that are attributed to the study drugs (Nivolumab or ONC201):

If a patient experiences a DLT, hold treatment (both drugs) until the adverse event reduces to a grade 1 or less and resume ONC201 at 1 dose level reduction. Nivolumab is not to be dose reduced.

If nivolumab is permanently discontinued due to toxicity, and the patient has had stable or responding disease, then ONC201 may be resumed when toxicity resolves to grade ≤ 1 . If the patient develops recurrent grade ≥ 3 toxicity while on single agent ONC201 after stopping nivolumab then ONC201 will be permanently stopped and the patient removed from protocol treatment.

6.4.2 DLT definitions phase Ib:

(Run-in Day -7, cycle 1 and pre-cycle 2), Events occurring in cycles 2-12+ in phase Ib or in phase II will be not be considered a DLT however both treatments must be held and once toxicity reduces to grade 1 or less, dose reduce ONC201:

Hematologic:

- Grade 4 neutropenia that persists for >7 consecutive days
- Febrile neutropenia (defined as neutropenia \geq Grade 3 and a body temperature 38.5°C)
- Grade ≥ 3 neutropenic infection
- Grade 4 thrombocytopenia (platelets $<25,000$ cells/mm 3) or Grade ≥ 3 thrombocytopenia with bleeding

Non-hematologic:

- Any other treatment related, clinically significant Grade ≥ 3 toxicity not classified under CTCAE blood or bone marrow with the exception of grade 3 nausea, vomiting, or diarrhea in patients who have received optimal treatment with antiemetics or anti-diarrheals and who do not downgrade to a grade 1 within 72 hours; Grade 4 (life threatening) diarrhea or vomiting will be considered DLTs, irrespective of the duration of the event. alopecia is not a DLT
- Delay of > 2 weeks secondary to a treatment related AE that is deemed possibly or definitely related to either drug
- Failure to receive at least 80% of the planned dose on ONC201 due to treatment related AEs (ONC201) in cycle 1 (5 doses ONC201 with run-in).

Although toxicities may be observed at any point during treatment, only those occurring during the defined DLT observation window of treatment that are considered DLTs will guide dose escalation decisions, expansion of a dose level, or evaluation of intermediate dose levels.

Patients will be monitored through all cycles of therapy for treatment-related toxicities, and all toxicities, including those occurring in beyond the DLT observation window, will be documented.

6.4.3 Dose de-escalation:

Dose de-escalation will proceed by a 3+3 design. Cohorts will be de-escalated in successive cohorts of 3 to 6 patients.

Patients failing to complete the first 4 weeks of treatment for reasons other than toxicity (e.g., lost to follow up, patient withdrawal, progression) will be replaced for the purpose of meeting the primary objective of this study.

Starting with the treatment of 3 patients at the planned dose cohorts described previously, the administration of ONC201 will follow traditional 3 + 3 dose de-escalation rules summarized below:

1. Dose level 1: Enroll 3 patients.
2. If 0 of 3 patients experience a DLT, 3 additional patients will be enrolled at that same dose cohort to confirm safety. If < 1 (no patients) of these 6 subjects encountered a DLT, then this dose level will be declared to be the MTD. This dose level will be expanded to treat 34 patients in phase II.
3. If 1 of 3 patients experience a DLT, 3 additional patients will be enrolled at that same dose cohort. If 2 or more of the 3-6 subjects within a cohort encounter a DLT, then the MTD has been exceeded and de-escalation will proceed to the next dose level (dose level 2 etc.). Only 2 dose reductions of ONC201 will be allowed.

6.5 ONC 201 Dose Delays/Holds Phase II: Dose Delays, Reductions and Interruptions for toxicities that are deemed related (some causality) to ONC201 During the Phase II Portion of the Study:

Adverse Event	Dose Adjustment
Grade 1 and 2	
 • No change in dose
Grade 3	
Hold ONC201
 
Resumption of ONC201 may continue as outlined below:
 
 • First occurrence: Hold ONC201 until \leq Grade 1. Resume ONC201 at one dose frequency cohort lower • Second occurrence: Hold ONC201 until \leq Grade 1. Resume ONC201 at one dose frequency cohort lower with \sim half the number of capsules administered followed by the administration of the other half of the capsules 6-12 hours later • Third occurrence: Off protocol therapy
Grade 4	
 • Off protocol therapy

If, however a patient experiences a “DLT toxicity” after cycle 2 or in the phase II portion it will not be considered a DLT, however: hold treatment (both drugs), once the toxicity reduces to a grade 1 or less, dose reduce (ONC201) and resume treatment, even though it will no longer be defined as a DLT.

On a day when Nivolumab and ONC201 are both due, if a patient is unable to receive Nivolumab based on section 6.6, ONC201 may be given alone, as long as the patient meets criteria for ONC201 dosing. If it is day 1 of a cycle, please also refer to section 6.3.

6.6 Dose delays for Nivolumab Phase Ib and Phase II:

Non-Immune mediated: All clinically significant (grade 3 or higher) hematologic and non-hematologic toxicities felt to have some causality to nivolumab must resolve to \leq grade 2 (excluding weight loss, weight gain, and alopecia) or to baseline prior to a patient receiving a subsequent dose (of Nivolumab). Any dose of nivolumab not administered will be skipped and not made up if outside of the \pm 2-day window.

Immune mediated: Adverse events (both serious and non-serious) associated with nivolumab may represent immunologic etiology.

Nivolumab must be held for suspected immune-mediated toxicities or severe/life-threatening AEs of particular interest as outlined in section below and immune-related toxicities in Appendix D. Please review both Sections (6.6 (below) and Appendix D) prior to infusion of nivolumab in any patient in whom immune-mediated toxicity is suspected.

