Across clinical trials of Opdivo administered as a single agent or in combination with ipilimumab, the following clinically significant immune-mediated adverse reactions, some with fatal outcome, occurred in less than 1.0% of patients receiving Opdivo: myocarditis, rhabdomyolysis, myositis, uveitis, iritis, pancreatitis, facial and abducens nerve paresis, demyelination, polymyalgia rheumatica, autoimmune neuropathy, Guillain-Barré syndrome, hypopituitarism, systemic inflammatory response syndrome, gastritis, duodenitis, sarcoidosis, histiocytic necrotizing lymphadenitis (Kikuchi lymphadenitis), motor dysfunction, vasculitis, aplastic anemia, pericarditis, and myasthenic syndrome.

If uveitis occurs in combination with other immune-mediated adverse reactions, consider a Vogt-Koyanagi-Harada-like syndrome, which has been observed in patients receiving Opdivo or Opdivo in combination with ipilimumab and may require treatment with systemic steroids to reduce the risk of permanent vision loss.

Infusion Reactions

In patients receiving Opdivo as a 60-minute intravenous infusion, infusion-related reactions occurred in 6.4% (127/1994) of patients. In a study assessing the pharmacokinetics and safety of a more rapid infusion, in which patients received Opdivo as a 60-minute intravenous infusion or a 30-minute intravenous infusion, infusion-related reactions occurred in 2.2% (8/368) and 2.7% (10/369) patients, respectively. Additionally, 0.5% (2/368) and 1.4% (5/369) of patients, respectively, experienced adverse reactions within 48 hours of infusion that led to dose delay, permanent discontinuation or withholding of Opdivo.

Management

Opdivo can cause severe infusion reactions, which have been reported in less than 1.0% of patients in clinical trials. Discontinue Opdivo in patients with severe or life-threatening infusion reactions.

Interrupt or slow the rate of infusion in patients with mild or moderate infusion reactions [see Dosage and Administration].

Embryo-Fetal Toxicity

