12.4 Definitions

An adverse event is any new, undesirable medical experience or change of an existing condition that occurs during or after treatment, whether or not considered product-related.

12.4.1 Attribution of the AE:

- Definite – The AE is *clearly related* to the study treatment.
- Probable – The AE is *likely related* to the study treatment.
- Possible – The AE *may be related* to the study treatment.
- Unlikely – The AE is *doubtfully related* to the study treatment.
- Unrelated – The AE is *clearly NOT related* to the study treatment.

Suspected adverse reaction:

BrUOG, for the sponsor-investigator, is required to report in an IND safety report any suspected reaction to the study treatment that is both serious and unexpected.

As per 21 CFR 312.32 (a), the FDA has defined a suspected adverse reaction as any adverse event where there is reasonable possibility that the drug may have caused the adverse event. A reasonable possibility means there is evidence suggesting a causal relationship between the drug and the adverse event.

A suspected adverse reaction outlines the possibility of the causal relationship between the event and the drug, whereas an adverse reaction means the drug caused the event.

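### Two DLT criteria do not match the attribution scale and the DLT lead-in, so a patient can lose 2 of 5 ONC201 doses to drug toxicity and still count as evaluable without a DLT

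*Combined protocol and SAP*

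**What the plan says.** The lead-in in section 6.4.1 defines a DLT as "any of the following AEs that are attributed to the study drugs (Nivolumab or ONC201"), that is, for either drug. Two of the criteria listed in 6.4.2 then set their own attribution condition:

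- Delay: "Delay of > 2 weeks secondary to a treatment related AE that is deemed possibly or definitely related to either drug".
- Lost doses: "Failure to receive at least 80% of the planned dose on ONC201 due to treatment related AEs (ONC201) in cycle 1", with the denominator given as "5 doses ONC201 with run-in".

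Section 12.4.1 sets a five-level attribution scale: Definite, Probable, Possible, Unlikely and Unrelated. The second level reads "Probable – The AE is *likely related* to the study treatment".

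Section 16.2 repeats the whole DLT list unchanged. It adds an evaluability rule: a patient with less than 80% of planned ONC201 in the first cycle is not evaluable for the MTD, provided the shortfall is unrelated to drug toxicity of any grade. If it is related, the reader is sent back to the DLT definition. Section 6.4.3 replaces only patients who fail to complete the first 4 weeks for reasons other than toxicity.

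The decision rule is also in 6.4.3. Two or more DLTs among the 3 to 6 patients of a cohort mean that the MTD is exceeded. Item 2 declares the MTD when none of six patients has a DLT. Section 16.2.1 uses the same event definition for the phase II suspension rule.

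**The concern.** The criteria that decide the ONC201 dose should classify every patient in the window as DLT, no DLT or not evaluable, and the attribution wording should match the scale that investigators use. Two mismatches prevent this.

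First, the delay criterion names the levels on either side of Probable but not Probable itself. Read literally, a weaker causal link counts and a stronger one does not.

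Second, the lost-dose criterion looks only at events attributed to ONC201. The lead-in and the delay criterion look at both drugs, and the evaluability rule in 16.2 looks at drug toxicity without naming a drug. A patient who falls below the protocol's own 80% threshold because of nivolumab toxicity can therefore stay in the denominator as a patient without a DLT. With at most six patients per level and a threshold of two, one such patient matters. The same definition then carries into the phase II safety monitoring.

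**Working it through.** The documents state no operating characteristic for the DLT definition, so there is no figure to reproduce. The check is textual, followed by an illustration of its consequence.

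**1. Attribution levels in the delay criterion.** Named: possible, definite. On the scale in 12.4.1 but not named: probable. Section 16.2 has the same wording, so the statistical section does not repair it. The omission matters only for events that are not already DLTs by grade.

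**2. Dose arithmetic.** Five ONC201 doses are planned (day -7 and days 1, 8, 15 and 22). Four of five is 80% and passes; three of five is 60% and fails. The loss of two doses is therefore enough to fall below the threshold.

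**3. A worked patient.** Take a grade 2 immune-mediated event attributed to nivolumab. Section 6.6 lists conditions for related immune events that must be met before either drug is given; grade 2 diarrhea and grade 2 transaminase elevation are examples that require a hold. Suppose ONC201 is missed on days 8 and 15 and resumed on day 22, and the day 15 nivolumab is skipped, so that the next infusion falls on cycle 2 day 1 (day 29).

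| Rule | Applied to this patient | Result |
|---|---|---|
| General grade 3 or higher criterion | Grade 2 | Not met |
| Delay over 2 weeks | ONC201: 22 - 8 = 14 days; nivolumab: 29 - 15 = 14 days | Not met |
| Lost ONC201 doses | 3/5 = 60%, but attributed to nivolumab | Not met |
| Non-evaluable (16.2) | Shortfall is related to drug toxicity | Does not apply |
| Replacement (6.4.3) | Reason is toxicity | Does not apply |

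The patient counts as evaluable without a DLT. This assumes that delay is counted from the missed due date; the protocol does not say how it is counted.

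**4. Effect on the decision.** One unscored patient turns 2/6 (exceeded) into 1/6 (not exceeded), or 1/6 into the 0/6 that item 2 of 6.4.3 requires.

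**5. Illustration.** Assume a true rate of limiting toxicity of 1/3 and let s be the share not scored. The counted rate is p = (1/3)(1 - s). Neither value is in the documents. Then

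- P(at most 1 of 6) = (1 - p)^6 + 6p(1 - p)^5
- P(0 of 6) = (1 - p)^6

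| s | p | P(at most 1/6) | P(0/6) |
|---|---|---|---|
| 0% | 0.333 | 0.088 + 0.263 = 0.351 | 0.088 |
| 5% | 0.317 | 0.102 + 0.283 = 0.385 | 0.102 |
| 25% | 0.250 | 0.178 + 0.356 = 0.534 | 0.178 |

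Both columns are needed because 6.4.3 states the 0/6 rule explicitly and gives no explicit clearing rule for 1/6.

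**The case against.** The case for leaving the text alone has several good parts.

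- *The missing level is only a slip.* The delay criterion already requires a treatment-related event, and its two levels can be read as the ends of a range. This is probably what was meant. What remains is that a criterion that drives de-escalation should not depend on the reader repairing it.
- *The ONC201 restriction may be deliberate.* ONC201 is the only drug that is de-escalated, nivolumab is never reduced, and the phase Ib objective is the ONC201 dose. That is a fair reason for the restriction. It does not explain the wider lead-in, or why 16.2 sends any toxicity-related shortfall back to a DLT definition that does not capture it.
- *The gap is narrow.* Clinically significant non-hematologic events of grade 3 or higher related to either drug mostly count, and so do delays over 2 weeks related to either drug. Several sections allow ONC201 alone while nivolumab is held. Section 6.6.3 puts the usual onset of immune events at 3 to 10 weeks, and the DLT window covers only 4 weeks of nivolumab. All of this stands.
- *Six patients are not the only safeguard.* Section 6.4 lets emerging toxicity data influence the RP2D, the synopsis plans an interim safety analysis after 12 patients, and the DSMB reviews cumulative toxicity. These soften the consequence but do not correct DLT scoring.

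A reader might also infer that the list excludes every unlisted blood or marrow event, because the general criterion covers "toxicity not classified under CTCAE blood or bone marrow with the exception of grade 3 nausea, vomiting, or diarrhea" events as its only exception, and that aplastic anemia therefore can never be a DLT. The documents do not support that. Marrow failure with prolonged grade 4 neutropenia, febrile neutropenia, grade 4 thrombocytopenia, or thrombocytopenia of grade 3 or higher with bleeding is a DLT. The delay criterion has no blood exclusion, although it sits under the non-hematologic heading. Section 2.2.3 does name aplastic anemia ("vasculitis, aplastic anemia, pericarditis, and myasthenic syndrome"), but its remark on fatal outcomes covers the whole list of reactions, each below 1.0%. Which hematologic events limit dose is a clinical choice.

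**Conclusion.** The two attribution mismatches are real and appear in both 6.4.2 and 16.2. The first is likely a drafting slip. The second leaves a definable patient, with 60% of planned ONC201 received because of study-drug toxicity, who is neither a DLT nor non-evaluable.

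The size cannot be fixed from the documents. Under an assumed true rate of 1/3, the chance of at most one counted DLT in six moves from 35% to about 38% if 5% of limiting events go unscored, and to 53% if 25% do. Under the written no-DLT-in-six rule, it moves from 9% to 18% at the 25% share. A reader might take the rise to 53% as the expected effect. It is not: the 25% share is an assumption, and the narrowness of the gap makes small shares plausible. Nor do the documents support saying that six patients alone fix the RP2D.

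The correction is worth making because the same definition drives de-escalation and the phase II suspension rule, and because it is cheap.

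**What to change.** Three passages should be reconciled, with the clinical team deciding the content:

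1. The attribution wording of the delay criterion in 6.4.2 and 16.2 with the scale in 12.4.1, so that the status of a delay rated probable is stated.
2. The drug attribution of the 80% criterion with the lead-in in 6.4.1 and with the evaluability rule in 16.2. Each patient below 80% because of drug toxicity should end up either as a DLT or as non-evaluable and replaced.
3. The blood and bone-marrow exclusion with section 2.2.3 and the nivolumab discontinuation list in 6.6.1. The clinical team should confirm that they are consistent. For example, 6.6.1 requires permanent discontinuation for drug-related grade 3 thrombocytopenia lasting more than 7 days even without bleeding, and that event is not on the DLT list.

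The cost is a few phrases in 6.4.2 and 16.2, which must stay identical. DLTs, or replaced patients, may become slightly more frequent.

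### In phase II, the Section 6.5 table takes ONC201-related Grade 4 toxicity off therapy, while the text beneath it, 6.4.1 and 16.2.1 say to reduce and resume after DLT-type events, Grade 4 included

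*Combined protocol and SAP*

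**What the plan says.** The heading of Section 6.5 limits its table to "toxicities that are deemed related (some causality) to ONC201 During the Phase II Portion of the Study". Grades 1 and 2 need no change, Grade 3 has a stepwise rule, and Grade 4 is "Off protocol therapy", with no exception in the row.

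The paragraph immediately under the table deals with DLT-type toxicity after cycle 2 or in phase II. Such an event no longer counts as a DLT, but the site is told to "hold treatment (both drugs), once the toxicity reduces to a grade 1 or less, dose reduce (ONC201) and resume treatment". Section 6.4.1 has the same rule, beginning "If, however a patient experiences one of the below toxicities after cycle 2 or in the phase II portion it will not be considered" dose-limiting. Section 16.2.1 repeats it and words it as something the patient's management must follow. The lead-in to 6.4.2 says "both treatments must be held and once toxicity reduces to grade 1 or less, dose reduce ONC201", without stating that treatment resumes.

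The DLT list in 6.4.2 includes "Grade 4 neutropenia that persists for >7 consecutive days", Grade 4 thrombocytopenia, and Grade 4 diarrhea or vomiting of any duration. It also takes in other treatment-related, clinically significant non-hematologic toxicity of Grade 3 or higher, apart from a stated exception for some Grade 3 gastrointestinal events.

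**The concern.** A DLT-type Grade 4 event in phase II that is related to ONC201 meets the conditions of both rules. One ends protocol therapy; the other requires re-treatment at a lower ONC201 dose after recovery. Under 6.2, permanently stopping ONC201 for toxicity also stops nivolumab, so the whole regimen turns on which paragraph the site applies. Two sites could manage the same event in opposite ways, each citing the protocol, and each would deviate from another part of it. The decision concerns re-exposure after a Grade 4 event, so the wording should leave no room for choice.

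**Working it through.** No arithmetic applies. The check sets the rules side by side for one case: a phase II patient with Grade 4 thrombocytopenia, judged related to ONC201 and not immune-mediated.

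| Section | Does it cover the case? | Instruction |
|---|---|---|
| 6.5 table, Grade 4 row | Yes: ONC201-related, phase II | Off protocol therapy |
| 6.5, paragraph under the table | Yes: on the DLT list, phase II | Hold both drugs, reduce ONC201, resume |
| 6.4.1 | Yes: same condition | Hold both drugs, reduce ONC201, resume |
| 16.2.1 | Yes: same condition, worded as required | Hold both drugs, reduce ONC201, resume |
| 6.4.2, lead-in | Yes | Hold both drugs, reduce ONC201 |

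The resume wording in 6.4.1, 6.5 and 16.2.1 is essentially one sentence used three times, so the comparison is one rule against one rule, not a vote of three to one.

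**Does another section settle it?**

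1. *Section 6.6, immune-mediated events.* The list there applies to immune-mediated events and does not name thrombocytopenia; 6.6.11 removes patients with other Grade 4 immune-mediated events. An unsure investigator is to treat an event as immune-mediated until that is ruled out. Once it is ruled out, these rules no longer apply.
2. *Section 6.6, non-immune events, and 6.6.1.* Both govern nivolumab: when the next dose may be given, and when it stops for good. Neither says what happens to ONC201.
3. *Sections 6.2 and 6.4.1 after nivolumab is stopped.* ONC201 may be restarted in patients with stable or responding disease. This is permissive and has no Grade 4 exclusion, so it does not resolve the conflict.
4. *Section 9.* It removes a participant when any listed criterion is met, including a toxicity that an earlier section makes a reason to stop. This leans toward the table, but it refers back to the sections that disagree.

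**Can the paragraph be read as an exception to the table?** Its opening words invite this, but the result is not sensible. ONC201-related, non-immune Grade 4 neutropenia of 7 days or less is not itself on the DLT list, so the table would end therapy. The same event lasting more than 7 days is on the list, so the patient would be re-treated. The longer event would get the more lenient rule. Because the list takes in nearly all clinically significant related non-hematologic events of Grade 3 or higher, the Grade 4 row would also be almost empty outside hematology.

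**Phase Ib.** The 6.5 table does not cover phase Ib. There, 6.4.1 says after a DLT to "hold treatment (both drugs) until the adverse event reduces to a grade 1 or less and resume ONC201 at 1 dose level reduction". That has no Grade 4 exception either, but no table row contradicts it.

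**The case against.** The best counter-argument is that Section 9 already answers the question. The Grade 4 row is a toxicity reason to stop, one reason is enough, and an instruction to resume presupposes a patient still on protocol therapy. This has force: it makes removal the more natural reading, and the fix below adopts it. It does not dispose of the point, because Section 9 ranks neither rule and 16.2.1 states hold, reduce and resume as a requirement.

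A second argument is that the protocol reports ONC201 as well tolerated. Section 12.2 describes 150 treated patients with a single dose reduction, for Grade 3 neutropenia that did not recur, and describes possibly related events as mild or moderate. That context suggests such Grade 4 events may be uncommon. It does not describe this combination, and an uncommon event still needs one rule.

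A reader might also infer that the conflict is strictly confined to non-immune events. The documents do not support that: the resume text has no immune carve-out, and 6.4.1 covers events attributed to either drug. What can be said is that the clash is clearest on the non-immune path, because 6.6 and 6.6.11 provide separate removal rules on the other.

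**Conclusion.** The inconsistency is real and the protocol is wrong as written. For an ONC201-related, DLT-type Grade 4 event in phase II, the Grade 4 row of 6.5 and the resume text in 6.5, 6.4.1 and 16.2.1 give opposite instructions, and nothing expressly says which prevails. The conclusion rests on the wording alone and on the event being attributed to ONC201.

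There is no numerical size to report. A reader might infer that a known share of patients would be re-treated, or that PFS would be biased. The documents give no Grade 4 rate for the combination, so neither follows. Nor should the conditional restart rule in 6.2 and 6.4.1 be counted as a separate mandated outcome: it depends on nivolumab having been stopped, and it permits rather than directs.

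**What to change.** Let the Grade 4 row of 6.5 govern.

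- In 6.4.1, 6.4.2, the paragraph under the 6.5 table and 16.2.1, add: *except ONC201-related Grade 4 events in phase II, which follow the Grade 4 row of 6.5 (off protocol therapy)*.
- In 6.2 and 6.4.1, state that the rule permitting ONC201 to restart after nivolumab is stopped does not apply to those events.
- In the Grade 4 row, name the laboratory-only exceptions already tolerated elsewhere: Grade 4 neutropenia of 7 days or less (excepted for nivolumab in 6.6.1) and isolated Grade 4 amylase or lipase elevation (allowed to continue in 6.6 and 6.6.6).
- Leave the immune-mediated rules in 6.6 to 6.6.11 unchanged. A blanket Grade 4 removal rule reaching immune-mediated events would override the amylase and lipase allowance.

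The cost is an amendment of a few sentences, with no change to sample size, endpoints or analysis. The downside is small: some patients who recover from a Grade 4 event could not resume, unless the event is a named exception.
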